1.0 Objectives / Specific Aims

- Purpose: Evaluate difference in postoperative opiate consumption in patients receiving a lateral quadratum lumborum (QL) block versus pericapsular nerve group (PENG) with lateral femoral cutaneous (LFC) nerve block for analgesia after hip arthroplasty.
- Hypothesis: The combination of PENG and LFC blocks will provide superior analgesia to the lateral QL block.

2.0 Background

The quadratus lumborum block is a fascial plane block. Originally described for abdominal surgery, numerous publications have highlighted the effectiveness of quadratus lumborum blocks as an analgesic technique for hip fracture and hip arthroplasty [1-4]. The pericapsular nerve group (PENG) block has been more recently described [5,6] and has demonstrated improved analgesia versus no block [7], and similar analgesia with improved motor function versus fascia iliaca block [8] or femoral nerve block [9]. The PENG block is commonly combined with a lateral femoral cutaneous (LFC) nerve block for coverage of the lateral thigh incision.

3.0 Intervention to be studied

- The lateral QL, PENG, and LFC blocks are already performed daily at MUSC as part of our standard perioperative care for patients undergoing hip arthroplasty. Currently, selection of the block type is dependent on the team caring for the patient that day, and studies have not compared QL and PENG+LFC blocks for postoperative analgesia after hip arthroplasty.
- **QL blocks:** The lateral QL block is performed by injecting local anesthetic deep to the transversus abdominus aponeurosis and superficial to the fascia transversalis with direct ultrasound guidance. After completing consent, placing monitors and providing mild sedation, the patient is positioned laterally and the muscular anatomy (external oblique, internal oblique, transverse abdominis, quadratus lumborum and latissimus dorsi muscles) identified. After placing a subcutaneous skin wheel with lidocaine, a blunt regional anesthesia needle is inserted using in-plane ultrasound guidance. Local anesthetic is deposited incrementally with frequent aspiration in the anterolateral border of the quadratus lumborum muscle at the junction of the transversalis fascia, outside the anterior layer of the thoracolumbar fascia and superficial to the fascia transversalis.
- **PENG block:** The pericapsular nerve group (PENG) block is an ultrasound-guided approach, first described by Giron-Arango et al. for the blockade of the articular branches of the femoral, obturator and accessory obturator nerves that provide sensory innervation to the anterior hip capsule [5,6]. In the PENG block, a low-frequency, curvilinear probe is used to visualize the anterior inferior iliac spine, iliopsoas tendon, and iliopubic eminence. After placing a subcutaneous skin wheel with lidocaine, a blunt regional anesthesia needle is inserted using in-plane ultrasound guidance. The needle is advanced until the tip lies on the lateral and inferior margin of the iliopsoas tendon between the anterior inferior iliac spine (lateral) and iliopubic eminence (deep).
- **Risks:** Risks of both blocks are similar. In general, all blocks have the risks of infection, bleeding, or local anesthetic toxicity (LAST). Infection risk is minimized

by utilizing appropriate antiseptic and sterile technique as is standard for any regional procedure. The risk of LAST is a risk with any regional procedure and is minimized by frequent aspiration, incremental local anesthetic injection and vital signs monitoring throughout. As for any truncal block, the QL block also has the risk of bowel perforation as it is higher in the abdominal wall. This risk is minimized with real time US visualization. The PENG block is located closer to the femoral nerve, and local anesthetic could spread to the femoral nerve with medial or superficial injection.

- **Current practice:** Both QL and PENG blocks are utilized at MUSC daily for postoperative pain following hip arthroscopy, arthroplasty, and hip fracture. Our current practice in patients receiving a PENG block includes also blocking the lateral femoral cutaneous (LFC) nerve for coverage of the lateral thigh incision.
- We hypothesize that PENG+LFC blocks will reduce opioid consumption following hip arthroplasty compared with lateral QL blocks.

4.0 Study Endpoints

- The primary outcome will be postoperative cumulative opioid consumption (in IV morphine mg equivalents: IV MME) over time, up to 72 hours postoperatively. Cumulative opioid consumption will be evaluated at in PACU, and through 72 hours post-op.
- Secondary outcomes: Postoperative pain score measures on the visual analog scale (VAS) captured in the preoperative area, PACU, and through 72-hours post-op.
- Additional outcomes of interest include time to first ambulation, functional and mobility outcomes, PACU duration, patient satisfaction, and opioid related side effects.

5.0 Inclusion and Exclusion Criteria/ Study Population

Inclusion Criteria

- Age greater than or equal to 18 years old
- Ambulatory patients undergoing elective hip arthroplasty (planned same day discharge or observation 23 hours or less)

Exclusion Criteria

- Local anesthetic allergy
- Subjects with a weight less than 40kg
- Subjects that are unable or choose not to give informed consent
- Known preoperative substance abuse

6.0 Number of Subjects

A total of 106 subjects will be included.

7.0 Setting

- MUSC perioperative areas.

8.0 Recruitment Methods

- For patients presenting to a preoperative clinic visit, information regarding the study will be presented to subject during their surgical consultation in the form of a flyer and informed consent document. Subjects will be educated on the role of regional anesthesia in postoperative analgesia. Subjects will be given ample time to consider participating in the surgery and asking questions. On the day of surgery, subjects may then choose to provide written consent or decline to participate. For patients without a surgical consult, the study will be presented on the day of surgery and will be given enough time to read the consent and consider participation.
- Subjects will be enrolled on the day of surgery in the preoperative holding area.

9.0 Consent Process

After discussion in a private area in the preoperative holding area regarding risks and benefits of the study and both block techniques, patients will be given adequate time to read the consent, think about participating, and ask questions. If agreeable to participating, consent will be obtained from patient by an IRB approved CITI certified study team member who is a physician or other medical clinician and has been trained on the protocol. Written consent will be completed once all questions are answered and inclusion and exclusion criteria verified. Copies of all documents will be provided to the patient. Once patients are consented, they will be assigned a study ID.

Randomization group (quadratus lumborum block versus pericapsular nerve group with lateral femoral cutaneous nerve blocks) will be determined by a randomization list created by a statistician and assigned based on the subject's study ID.

10.0 Study Design / Methods

- **Objective and outcomes:** Determine if PENG+LFC blocks reduce opioid consumption compared to a QL block after THA.
- **Design:** This prospective, blinded clinical trial will randomize subject to receive a PENG+LFC or QL block prior to THA. The randomization will be created by a statistician prior to subject enrollment.
- **Groups:** Subjects will be randomized to receive a preoperative PENG+LFC (n=53) or QL (n = 53) block prior to THA.
- Potential participants that are on the operating room schedule for THA will be screened for eligibility via chart review.

Baseline

- Once subjects have signed an informed consent, they will be assigned an enrollment number. Randomization will be created prior to the study starting with half of the research subject numbers being assigned to receive a PENG+LFC block, and the other half assigned to receive a QL block. Both blocks are considered our current standard of care. A study team member will open the envelope labeled with the subject's assigned study ID to reveal the randomization assignment.

- The participant's medical record will be reviewed for demographic data collection and durations (operative, PACU, hospital stay).
- Before placing the block, participants will be asked what their current pain score is by using a Visual Analog Scale (VAS) from 0-100, and complete the HOOS Jr, and PROMIS-10 Global Health questionnaires.

Randomization

- All subjects will be positioned, prepped, and sedated for the randomized regional anesthesia procedure in the preoperative holding area. The subject will be positioned in the supine position and pulse oximetry and blood pressure cuff placed for monitoring. As part of routine care, the subject will receive sedation for their comfort. All subjects would receive 30 ml of 0.25% ropivacaine in their nerve block regardless of randomization. The relevant anatomy will then be identified using ultrasound guidance and real time imaging. For both groups, ropivacaine will be injected slowly with frequent aspiration to rule out inadvertent intravascular needle placement. Local anesthetic injection will also be observed with real time ultrasound guidance. All participants, regardless of group assignment, will have subcutaneous numbing medication placed just below the skin at both block sites (skin wheal). This will be done so that participants and the research team collecting results will be blinded. Subjects, surgeons, and data collectors will all be blinded to the allocated group. Unblinded personnel will be the Anesthesia Attending placing the block and clinical staff assisting.
- In subjects randomized to the QL group, ultrasonography will be used to identify external oblique, internal oblique, transverse abdominus, and quadratus lumborum muscles. A needle will then be advanced under ultrasound guidance below the internal oblique aponeurosis and lateral to the quadratus lumborum muscle. Ropivacaine will be injected slowly with frequent aspiration to rule out inadvertent intravascular needle placement. Local anesthetic injection will also be observed with real time ultrasound guidance.
- In subjects randomized to the PENG+LFC group, ultrasonography will be used to identify the anterior inferior iliac spine, iliopsoas tendon, and iliopubic eminence. After placing a subcutaneous skin wheal with lidocaine, a needle will be advanced until the tip lies on the lateral and inferior margin of the iliopsoas tendon between the anterior inferior iliac spine (lateral) and iliopubic eminence (deep).

Post-Op and Follow-Up

The participant will be asked to provide their average pain score while at rest, and average pain score with movement in the specified time period using a visual analog scale from 0-100 with 100 being the worst. The first pain score will be recorded before they leave the PACU on the day of the procedure. Beginning the following morning, the participant will receive a text message link sent by Twilio's secure server that opens a survey housed in RedCap. The first text message will arrive at 9:00 AM and will follow the schedule in **Table 1**.

The follow-up text messages will also ask the patient the name, dose, and frequency of any pain medication taken in that time period. On Day 7, the text message survey will assess functional outcomes by using two different questionnaires. The patient will schedule at least two post-operative in-person follow up visits as standard of care. One visit at approximately 2-3 weeks post-op, and the other at approximately 6 weeks.

During these two visits the patient will complete the same functional questionnaires as they did at Baseline and on Day 7. This may be done in person at their standard of care post-op visits or may be contacted by study personnel to complete via telephone. Adverse events will also be collected throughout the study.

The text messages are sent from a secure server, Twilio, and are housed in REDCap. The set of questions will state what time window (example: 12:00 AM midnight the night prior to 12:00 PM noon the same day) to consider when answering the questions.

If the participant has been discharged from the hospital, they will answer these questions in the text message each day. If they are admitted to the hospital at these points in time, the information will be gathered from their chart for medications and asked verbally for pain scores and additional questions. Additional data will be recorded by physical therapy and surgical staff and pulled from the patient's medical record for data collection.

If the participant is unable or unwilling to receive text messages, they will be provided a paper document to record their data for the pre-determined intervals so when a study member contacts them, they are able to relay their answers back accurately.

Care in the perioperative period will otherwise be standardized. In the post-anesthesia care unit (PACU), hydromorphone or morphine will be titrated by the PACU nurse for the subject's comfort. Additionally, as standard of care, Physical Therapy will evaluate patients in the PACU before discharge.

An outline of study time points and assessments is shown in **Table 2**.

Table 1. Post-Op Follow Up Assessment Schedule

Post-Op Day	Time of Text Message	Data Collection Time Period
POD 0	Right before discharge	Waking up from surgery to discharge
POD 1-AM	9:00 AM	Discharge to 11:59 midnight prior
POD 1-PM	3:00 PM	12:00 AM midnight night prior to 12:00 PM noon same day
POD 2-AM	9:00 AM	12:01 PM noon day prior to 11:59 PM midnight night prior
POD 2-PM	3:00 PM	12:00 AM midnight prior to 12:00 PM noon same day
POD 3-AM	9:00 AM	12:01 PM noon day prior to 11:59 PM midnight night prior
POD 3-PM	3:00 PM	12:00 AM midnight prior to 12:00 PM noon same day

Table 2. Summary of Study Procedures and Follow-Ups	
Study Activities	Details/Assessments
Informed consent	
 Obtain informed consent
Baseline	
 Pre-Operative VAS Pain Score Quad Strength Pre-Op HOOS Jr PROMIS-10 Global Health
Randomization (day 0)	
 Confirm eligibility criteria Randomization
Randomization procedure (day 0)	
 Complete PENG or QL Block according to randomization allocation
Post-Op First Opportunity in PACU	
 Opioid Consumption
Ambulation (Assessed by Physical Therapy in PACU)	
 Time that first ambulation occurred in PACU Distance ambulated in PACU Quad Strength in PACU
Post-Op Day 1 9:00 AM (text message)	
 Opioid and pain medication consumption VAS Pain Score
Post-Op Day 1 3:00 PM (text message)	
 Opioid and pain medication consumption VAS Pain Score
Post-Op Day 2 9:00 AM(text message)	
 Opioid and pain medication consumption VAS Pain Score
Post-Op Day 2 3:00 PM (text message)	
 Opioid and pain medication consumption VAS Pain Score
Post-Op Day 3 9:00 AM (text message)	
 Opioid and pain medication consumption VAS Pain Score
Post-Op Day 3 3:00 PM (text message)	
 Opioid and pain medication consumption VAS Pain Score Satisfaction with analgesia Side Effects of nausea/vomiting, itching, over sedation, respiratory concerns related to opioids Adverse Events
Day 7 Post-Op 9:00 AM (text message)	
 HOOS JR PROMIS-10 Global Adverse Events
Week 2-3 Post-Op (scheduled SOC clinic visit or telephone)	
 HOOS JR PROMIS-10 Global Adverse Events
Week 6 Post-Op (scheduled SOSC clinic visit or telephone)	
 HOOS JR PROMIS-10 Global Averse Events
After completion of 6-week post-op follow-up	
 All study activities complete

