11.0 Data Management

- **Sample size and power:** The primary outcome for assessing differences between PENG+LFC vs. QL blocks will be postoperative cumulative opioid consumption (in IV morphine mg equivalents; IV MME) over time, up to 72 hours postoperatively. Cumulative opioid consumption will be evaluated in PACU, and at 12-hour intervals during the first 72 hours of the postoperative window. Differences in cumulative opioid consumption over time between block groups will be assessed using a linear mixed model approach. The model will include fixed effects for treatment group, postoperative time, and the interaction between block group and postoperative time and a random subject effect to account for correlation between measures collected on the same patient over time. Differences between block types at each postoperative time will be evaluated using linear contrasts from the model. A previous study⁹ conducted at MUSC found mean IV MME at 12 hours postop in subjects undergoing THA with a QL block was 16 ± 12 MME. A sample size of 48 subjects per group with 9 repeated measures of opioid consumption provides 80% power to detect a difference in cumulative MMEs consumed postoperatively of 4 MMEs at significance level $\alpha = 0.006$ (Bonferroni adjusted for 9 pairwise comparisons between group) assuming a standard deviation of ± 12 MMEs, a first-order autoregressive correlation structure and correlation between observations on the same subject of $\rho = 0.33$. We will plan to enroll 53 subjects/group (106 total) to allow for 10% attrition.
- Postoperative VAS pain score captured in the preoperative area, PACU and 12-hour intervals during the first 72 hours of the postoperative window will be collected as a secondary outcome and will be evaluated using a LMM similar to the primary outcome. Additional outcomes of interest include time to first ambulation, functional and mobility outcomes, PACU duration, patient satisfaction, and opioid related side effects.

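### The single momentary pain score taken before the block matches neither of the two postoperative pain scores, and the plan does not say which of those two is the secondary outcome

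*Combined protocol and SAP*

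**What the plan says.** Section 10.0 (Baseline) sets the preoperative measure: before the block, "participants will be asked what their current pain score is by using a Visual Analog Scale (VAS) from 0-100". This is one score for the present moment, and it is not tied to rest or to movement.

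Section 10.0 (Post-Op and Follow-Up) sets the later measure. The patient reports "average pain score while at rest, and average pain score with movement in the specified time period", again on 0-100. The timing starts in recovery: "The first pain score will be recorded before they leave the PACU on the day of the procedure". For the text surveys, "The set of questions will state what time window" the patient should consider. Table 1 gives seven postoperative windows. Five are half-days of about 12 hours. The other two run from waking to discharge and from discharge to midnight.

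The outcome is named in two places. Section 4.0 lists "Postoperative pain score measures on the visual analog scale (VAS) captured in the preoperative area, PACU, and through 72-hours post-op". Section 11.0 has "Postoperative VAS pain score captured in the preoperative area, PACU and 12-hour intervals during the first 72 hours of the postoperative window", which "will be evaluated using a LMM similar to the primary outcome". The primary model has fixed effects for group, time and their interaction, plus a random subject effect. Table 2 lists a VAS pain score at each text message without dividing it into rest and movement.

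**The concern.** Sections 4.0 and 11.0 treat pain as one series running from the preoperative area to 72 hours. The data collected under section 10.0 do not form one series: there is one momentary value first, then pairs of window averages.

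Two things are at stake, both for the secondary outcome only.

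- **Which result is reported.** No section says whether the secondary result is rest pain, movement pain, an average of the two, or two results side by side. If this is settled after the data are seen, the reported result can depend on which score looks better.
- **Use of the baseline.** A preoperative score helps precision to the extent that it correlates with the later score. A momentary score of unspecified type is not like-for-like with either postoperative score, and the model named does not use it as a covariate in any case.

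**Working it through.** **1. Is there a figure in the plan to reproduce?** Not for VAS: the documents give no standard deviation, effect size, correlation or sample size for pain. The 48 per group in section 11.0 is for opioid consumption. It reproduces as a time-averaged difference. The mean of 9 AR(1) measures with correlation 0.33 has SD 12 × √0.2024 = 5.40, and a difference of 4 then needs 47 per group at α = 0.006, or 48 at 0.05/9. Nothing below changes it.

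**2. The definitions side by side.**

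| | Before block | Each postoperative window |
|---|---|---|
| Scores | one | two |
| Reference period | now | average over the window |
| Condition | not stated | rest; movement |
| Name in sections 4.0 and 11.0 | VAS pain score | VAS pain score |

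**3. Does the mismatch bias the group contrasts?** In a model with group, time (as categories) and their interaction, and with complete data, each group-by-time mean is estimated by its own sample mean. The preoperative row cannot move the later contrasts. A simulation with 48 per group and assumed VAS values agrees: the first postoperative rest-pain contrast was -8.69 with a matching baseline row, with a differently defined one, and with none. The preoperative row can still affect the variance and correlation estimates, the time effect and any change from baseline. With missing windows it can also reach the contrasts through the shared subject effect; the plan allows for 10% attrition.

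**4. Does the choice of score matter?** In the same simulation the first postoperative contrast was -8.69 for rest, -12.88 for movement and -10.79 for their average. The simulated effect was set larger for movement (-15 against -8), so this shows only that the choice matters if the block acts differently on the two scores. It is not evidence that it does.

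**5. What is a matching baseline worth?** With a baseline covariate whose correlation with the postoperative score is r, the residual variance factor is 1 − r². Both correlations below are assumptions, with r taken as the same at each time. For the momentary score assume r = 0.2, so the factor is 1 − 0.04 = 0.96.

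| Matching r | 1 − r² | Against momentary covariate: 0.96/(1 − r²) | Against no covariate: 1/(1 − r²) |
|---|---|---|---|
| 0.2 | 0.96 | 1.00 | 1.04 |
| 0.3 | 0.91 | 1.05 | 1.10 |
| 0.4 | 0.84 | 1.14 | 1.19 |
| 0.6 | 0.64 | 1.50 | 1.56 |

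The third column is the value of asking the matching question rather than using the momentary score as covariate: about 5% to 50% more patients for r from 0.3 to 0.6, and nothing if the correlations are equal. The last column compares with the plan as written, which names no covariate.

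**The case against.** The strongest reply is that this is an unfinished specification and not a faulty analysis. Section 11.0 names a type of model, section 4.0 speaks of measures in the plural, and two separate models would fit both texts. The single preoperative score is taken before the block in the same way in both arms, so it cannot favour one. The precision figures rest on assumed correlations and on a covariate the plan does not name. The primary outcome and sample size are untouched.

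All of that stands, and it rules out several stronger readings:

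- A reader might infer that rest and movement scores are mixed in one analysis. The documents do not say so; they are silent.
- A reader might infer that the baseline mismatch biases the block comparison. With complete data it does not (step 3).
- A reader might count two scores at seven windows and see a doubling of planned tests. The plan states no number of contrasts, and no multiplicity rule, for VAS.
- A reader might take movement pain as the intended lead because section 15.0 mentions motor function and earlier physical therapy. That section lists potential benefits; the stated objective is opioid consumption.
- A reader might object that inpatients are "asked verbally for pain scores and additional questions". The text does not say that no scale is shown, and eligible patients are planned for same-day discharge or at most 23 hours of observation, so few windows should be affected.

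The reply does not close two gaps: the secondary result is not identified, and neither postoperative score has a baseline of its own kind.

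**Conclusion.** The point holds as a cheap improvement to the secondary outcome. The plan collects a baseline that matches neither postoperative pain score, makes no stated use of it as a covariate, and does not say which score is the secondary result.

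The size cannot be fixed from the documents. The range of about 5% to 50% assumes r = 0.2 for the momentary score and 0.3 to 0.6 for a matching one, with baseline used as a covariate. Equal correlations would remove that gain. The case for naming the outcome does not depend on these figures.

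**What to change.** 1. Before the block, ask two questions, average pain at rest and average pain with movement, with the same 0-100 scale and wording as afterwards. Use a recall period close in length to the postoperative windows, about 12 hours; a 24-hour recall would not match Table 1.
2. In sections 4.0 and 11.0, define rest VAS and movement VAS as separate outcomes. Fit one mixed model to each, with postoperative times only as the outcome and the matching preoperative score as a covariate.
3. State before unblinding which of the two leads. The documents do not settle this, so the choice belongs to the investigators.
4. Divide the VAS entries in Table 2 into rest and movement.

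The cost is one extra baseline question, one extra model and small edits to the case report form. If baseline collection can no longer change, steps 2 and 3 can still be done before unblinding, with the current score as the covariate in both models. That settles which result is reported but gives up the like-for-like baseline.

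### Opioid side effects and satisfaction are solicited once, on the afternoon of post-op day 3, and as written that question looks back only to midnight

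*Combined protocol and SAP*

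**What the plan says.** Sections 4.0 and 11.0 list patient satisfaction and opioid-related side effects as additional outcomes of interest, below the primary outcome (cumulative opioid consumption) and the secondary outcome (VAS pain).

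Table 2 in Section 10.0 schedules both in a single row, the POD 3 3:00 PM text: "Satisfaction with analgesia" and "Side Effects of nausea/vomiting, itching, over sedation, respiratory concerns related to opioids". The row "Post-Op First Opportunity in PACU" lists opioid consumption only. The five earlier texts list medication use and VAS pain only.

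Table 1 gives the POD 3-PM text the data collection period "12:00 AM midnight prior to 12:00 PM noon same day". The follow-up text in Section 10.0 adds: "The set of questions will state what time window" to consider when answering. Neither place gives a separate recall period for side effects or satisfaction.

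Two other provisions bear on the point. Section 10.0 says that adverse events are collected for the whole study. Section 12.0 requires every new complaint or symptom since consent to go on the adverse event form, with start and stop dates.

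**The concern.** Reducing opioid use matters to patients partly because it may reduce opioid side effects, so this outcome helps a reader interpret the primary result. The plan places intravenous opioid exposure early: in PACU, "hydromorphone or morphine will be titrated by the PACU nurse for the subject's comfort". Its planning figure for early use is also substantial: a previous study "found mean IV MME at 12 hours postop in subjects undergoing THA with a QL block was 16 ± 12 MME".

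The scheduled question does not look at that period. Followed as written, a patient who vomited in PACU or was over-sedated on the first night, and was well by POD 3, would correctly answer no. Events asked about only on the last morning are likely to be few in both groups. A report of no difference in side effects could then come partly from the recall window rather than from the blocks. Satisfaction has the same ambiguity: the rating may describe one morning or the whole course. Neither can be repaired once the data are in.

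**Working it through.** The plan gives no incidence, power or precision figure for side effects or satisfaction. Its only power statement (Section 11.0) concerns opioid consumption and does not bear on this point. The check is therefore a reading of the schedule, clock arithmetic, and an illustration.

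**1. Schedule (Tables 1 and 2, Section 10.0)**

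| Assessment | Window in Table 1 | Side effects or satisfaction listed in Table 2? |
|---|---|---|
| PACU / before discharge | waking to discharge | no |
| POD 1, 9:00 AM | discharge to midnight | no |
| POD 1, 3:00 PM | midnight to noon | no |
| POD 2, 9:00 AM | noon to midnight, day before | no |
| POD 2, 3:00 PM | midnight to noon | no |
| POD 3, 9:00 AM | noon to midnight, day before | no |
| POD 3, 3:00 PM | midnight to noon | yes, both |

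The items appear in 1 of 7 windows, the last. The first Table 2 row that lists adverse events is this same POD 3 text.

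**2. What the window covers.** The time at which surgery ends is not in the documents. I assume 09:00 to 17:00. If surgery ends at hour E on day 0, midnight at the start of POD 3 is 72 − E hours later and noon is 84 − E hours later.

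- E = 9: hours 63 to 75. Overlap with the first 72 hours is 72 − 63 = 9 hours, and 9/72 = 12.5%.
- E = 17: hours 55 to 67. Overlap is 12 hours, and 12/72 = 16.7%.

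Across the assumed range, none of the first 55 hours falls in the window.

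**3. Illustration of the consequence.** Every incidence below is assumed; the documents give none. The test is a pooled two-proportion z-test, two-sided 5%, with 53 per group (Section 10.0). Expected events = 53 × (p1 + p2). Power is the exact sum of binomial probabilities over outcomes with |z| > 1.96.

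| Assumed setting | p1 v p2 | Expected events | Power |
|---|---|---|---|
| Early period | 30% v 15% | 53 × 0.45 = 23.9 | 47% |
| Early period | 40% v 20% | 53 × 0.60 = 31.8 | 63% |
| POD 3 morning | 10% v 5% | 53 × 0.15 = 8.0 | 15% |
| POD 3 morning | 5% v 2.5% | 53 × 0.075 = 4.0 | 8% |

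Each row is the same halving of risk. The contrast between early and late rows comes from the incidences chosen. It also supposes that the midnight-to-noon window applies to these items and that adverse event records add nothing. It shows the direction of the problem, not its size in this trial.

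**The case against.** **Adverse event reporting covers the gap.** A reader might infer from Table 2 that the trial misses early side effects altogether. The documents do not support that. Consent precedes the block, so vomiting in PACU is a new symptom that Section 12.0 requires on the adverse event form with dates. Section 10.0 also provides for data from the medical record and for verbal questions to patients still in hospital. This stands as a partial safeguard. It is not a scheduled question: Table 2 shows no adverse event prompt before POD 3, and the verbal questions follow the same schedule. Section 5.0 enrolls patients planned for same-day discharge or at most 23 hours of observation, so most of the gap would be spent at home, where patients must volunteer symptoms. The plan does not say that the side-effect outcome will be taken from the adverse event form, and that form does not capture satisfaction.

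**The window may not be meant for these items.** Section 10.0 ties the time period explicitly to pain scores and pain medication. The survey wording is not in the documents, and one question at the end of the series could be an overall rating. The adverse event item in the same row can hardly be limited to one morning. This also stands: applying midnight to noon to side effects and satisfaction is an inference. But the general sentence about the question set covers them on its face, and no other period is written.

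**Most opioid use is early.** A reader might infer this, but the documents give no 72-hour total and no block duration. They support substantial early use, no more.

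**Asking earlier would not make the comparison well powered.** True: under the assumed 30% v 15%, power is 47% with 53 per group and 43% with the 48 evaluable per group of Section 11.0. A null result would be inconclusive either way. That is no reason to keep a window that could also lower the count.

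**Conclusion.** The point holds in a limited form. The only solicited side-effect and satisfaction questions come at POD 3, and as written they look back 12 hours. They leave out PACU and POD 0 to 2, including the period of titrated intravenous opioid. Early side effects would rest on unsolicited reporting and would probably be under-counted in both groups, while satisfaction has no clear reference period.

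The coverage of 12.5% to 16.7% of the first 72 hours rests on the assumed 09:00 to 17:00 end of surgery and on Table 1's window applying to these items. The power figures are illustrations from assumed incidences, not estimates for this trial.

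The consequence is confined to two additional outcomes. The primary and secondary analyses are untouched. It is worth correcting because these are named outcomes and the remedy is a small edit.

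**What to change.** At minimum, word the POD 3 side-effect and satisfaction items to ask about the time *since your surgery*, so that neither takes on the midnight-to-noon window.

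Preferably, also add the four side-effect items (nausea/vomiting, itching, over-sedation, respiratory concerns) as tick-boxes to the PACU assessment and to each existing text through POD 3, each with that assessment's own window. Define the outcome as any event from PACU through POD 3 and compare it by group. State whether adverse event records contribute to that outcome.

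The minimum change is a line of survey wording. The fuller change is a protocol and REDCap form edit with no extra visits. Its downside is slightly longer surveys, which deserves some care because the same texts carry the primary outcome; if completion is a worry, the minimum change alone removes the main ambiguity.
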